8.2 Stopping Criteria

Regional nodal recurrences occur in 1 - 5% of patients with early stage breast cancer who have undergone mastectomy or breast conserving therapy (Fisher, Anderson et al. 2002; Moran and Haffty 2002; Harris, Hwang et al. 2003). While most nodal recurrences occur within the first five years after treatment, nodal recurrences have been documented for more than twenty years after completion of treatment (Lukens, Vapiwala et al. 2009).

Based on this data, a stopping rule for regional node recurrences will be implemented with an evaluation after every 21 patients are observed for at least 1 year post treatment. The schema is described in Section 14. This rule allows early stopping based on an excess of incidence of regional node recurrences (greater than 5% of patients).

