13 DATA REPORTING / REGULATORY CONSIDERATIONS

13.1 Monitoring Plan

An internal Data and Safety Monitoring Committee (DSMC) of the NYUCI is the monitoring board for this study. The committee will review safety at scheduled intervals (not less than once/year) and at the time of planned interim analyses described in Section 9 according to the NYUCI DSMC Charter.

13.2 Stopping Rules (for the individual patient and for the study as a whole)

If safety concerns arise, the DSMC will identify these concerns and recommend modification or termination of the clinical trial. In case of grade 3 acute skin toxicity, the dose per fraction of the remaining treatment fractions will be reduced to 2 Gy/fraction until completion. The clinical trial will be stopped early if regional nodal recurrence is greater than expected (5% of patients) as described in Section 14.

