Safety Stopping Rule; In addition, regional nodal recurrence will be monitored as the study progresses. If we enroll 104 patients over a three year period with follow-up of one year after the last patient is entered, the regimen will be considered ineffective if the null hypothesis that the proportion of regional nodal recurrences is 5% is rejected at an interim review.

Regional nodal recurrence is defined as recurrence within the axilla, level III or supraclavicular nodes, documented by PET-CT imaging and/or biopsy.

With 5 interim looks (every 21 patients who are followed for at least 1 year), with Pocock stopping boundaries, the trial would be stopped if the observed numbers of regional nodal recurrences are greater than or equal to 1 of the first 21 patients, and greater than 2, 4, 6, and 8 respectively at the second – fifth looks with an overall 1-sided alpha level of 0.05 and power of 0.62 [Calculations from EAST 5.2, Cytel, Inc., 2008].

REFERENCES

Archambeau, J. O., R. Pezner, et al. (1995). "Pathophysiology of irradiated skin and breast." *Int J Radiat Oncol Biol Phys* **31**(5): 1171-85.

Arnold, N., E. Gross, et al. (1999). "A highly sensitive, fast, and economical technique for mutation analysis in hereditary breast and ovarian cancers." *Hum Mutat* **14**(4): 333-9.

Atencio, D. P., C. M. Iannuzzi, et al. (2001). "Screening breast cancer patients for ATM mutations and polymorphisms by using denaturing high-performance liquid chromatography." *Environ Mol Mutagen* **38**(2-3): 200-8.

Baillet, F., M. Housset, et al. (1990). "The use of a specific hypofractionated radiation therapy regimen versus classical fractionation in the treatment of breast cancer: a randomized study of 230 patients." *Int J Radiat Oncol Biol Phys* **19**(5): 1131-3.

Bar Ad, V., A. Cheville, et al. (2009). "Time Course of Mild Arm Lymphedema After Breast Conservation Treatment for Early-Stage Breast Cancer." *Int J Radiat Oncol Biol Phys*.

Barendsen, G. W. (1982). "Dose fractionation, dose rate and iso-effect relationships for normal tissue responses." *Int J Radiat Oncol Biol Phys* **8**(11): 1981-97.

Bartelink, H., J. C. Horiot, et al. (2001). "Recurrence rates after treatment of breast cancer with standard radiotherapy with or without additional radiation." *N Engl J Med* **345**(19): 1378-87.

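### The printed nodal-recurrence stopping counts carry a 0.70 chance of stopping at the 5% null, not the stated 1-sided alpha of 0.05

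*Combined protocol and SAP*

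**What the plan says.** The safety stopping rule at the end of Section 14.5 tests a null of 5% regional nodal recurrence: "the regimen will be considered ineffective if the null hypothesis that the proportion of regional nodal recurrences is 5% is rejected at an interim review". The design is "With 5 interim looks (every 21 patients who are followed for at least 1 year), with Pocock stopping boundaries". The trial stops if recurrences are "greater than or equal to 1 of the first 21 patients, and greater than 2, 4, 6, and 8 respectively" at the second to fifth looks, "with an overall 1-sided alpha level of 0.05 and power of 0.62". EAST 5.2 is cited as the source. No alternative proportion is given for this rule.

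Two other sections describe the same rule. Section 8.2 gives the background ("Regional nodal recurrences occur in 1 - 5% of patients with early stage breast cancer") and the purpose: "This rule allows early stopping based on an excess of incidence of regional node recurrences (greater than 5% of patients"). Section 13.2 says: "The clinical trial will be stopped early if regional nodal recurrence is greater than expected (5% of patients) as described in Section 14".

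**The concern.** A 1-sided test for an excess over 5% cannot reject on an observed proportion below 5%, yet the first limit is met by 1/21 = 4.8%. A Pocock rule also applies one constant critical value at every look, and these counts do not look as though they come from a single constant.

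The counts are what the DSMC would apply. If they do not carry the stated alpha, a committee that believes it accepted a 5% risk of stopping without cause is running a much larger one. A single early event could close the trial and have the regimen called ineffective when recurrence is no higher than expected.

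**Working it through.** **Inputs (Section 14.5).** Null proportion 0.05. Looks after 21, 42, 63, 84 and 104 patients (five blocks of 21 make 105; both were run). Limits read as cumulative counts: stop at ≥1, ≥3, ≥5, ≥7, ≥9. Stated 1-sided alpha 0.05; stated power 0.62.

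**First look by hand.** P(at least 1 of 21 | p = 0.05) = 1 − 0.95^21 = 0.659. This look alone uses about 13 times the stated overall alpha (0.659/0.05).

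**All five looks.** Exact recursion: add the binomial count for each new block to the running total, remove the paths that have reached the limit, and carry the rest forward.

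| Look | Patients | Stop at | Observed proportion | z under the null | P(stop here), p = 0.05 |
|---|---|---|---|---|---|
| 1 | 21 | ≥1 | 0.048 | −0.05 | 0.659 |
| 2 | 42 | ≥3 | 0.071 | 0.64 | 0.029 |
| 3 | 63 | ≥5 | 0.079 | 1.07 | 0.009 |
| 4 | 84 | ≥7 | 0.083 | 1.40 | 0.003 |
| 5 | 104 | ≥9 | 0.087 | 1.71 | 0.001 |
| Total | | | | | 0.702 |

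Here z = (x/n − 0.05)/√(0.05 × 0.95/n). With the last look at 105 the total is again 0.702, and a simulation of 1,000,000 trials agreed. The stated alpha is not reproduced.

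**Pocock shape.** For five looks at 1-sided 0.05 the constant is z = 2.12. The limit in events is 0.05n + 2.12√(0.05 × 0.95 × n), which gives 3.2, 5.1, 6.8, 8.4 and 9.9. The printed counts lie below these at every look, and their z-values rise from −0.05 to 1.71 instead of staying constant.

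**Other readings of the sentence, P(stop) at p = 0.05.**

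| Reading | P(stop) |
|---|---|
| First look as more than 1 | 0.45 |
| At-or-above at every look (≥1, 2, 4, 6, 8) | 0.78 |
| First look dropped | 0.39 |
| Counts per block, not cumulative | 0.69 |
| Limits >2, >4, >6, >8 moved to looks 1–4 | 0.125 |
| Final look only | 0.08 |

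None reaches 0.05.

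**Power.** With no stated alternative, 0.62 cannot be checked directly. The printed rule stops with probability 0.96 at an assumed 10%. It stops with probability 0.62 at a true proportion of about 4.2%, which is below the null.

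**Sensitivity to the true proportion (assumed values).**

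| True proportion | 5% | 4% | 3% | 2% | 1% | 0.5% |
|---|---|---|---|---|---|---|
| P(stop) | 0.70 | 0.60 | 0.49 | 0.35 | 0.19 | 0.10 |

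The probability passes one half at about 3.1%. It falls to 0.05 only at about 0.24%.

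**The case against.** The strongest reply is about consequence. The 1–5% background in Section 8.2 carries no time point, and the same section says most nodal recurrences occur within the first five years, whereas patients enter a look after at least one year. The proportion visible at a look may be well under 5%, perhaps under 1%, so 0.70 does not forecast how often the trial would stop wrongly. That stands, and it is why the range is shown. It does not rescue the stated alpha, which is defined at the null.

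Second, about 94% of the 0.70 (0.659/0.702) comes from one number, and stopping on a single early event can be a deliberate, cautious choice. That is fair as a policy. But the plan presents the count as a Pocock limit with alpha 0.05, and looks two to five alone still give 0.39.

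Third, a transcription slip from the software output is plausible: moving the last four limits to looks one to four gives 0.63 at an assumed 10%, close to the stated 0.62. That reading still has alpha 0.125, and the printed counts are the ones that would be applied.

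Fourth, the language is not uniformly mandatory. Section 8.2 says only that the rule permits stopping, and Section 13.2 has the DSMC recommend changes when safety concerns arise. However, Sections 13.2 and 14.5 both state this rule as one that stops the trial.

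Finally, this is a monitoring rule, not a primary endpoint. A false stop would reduce the sample but would not alter how the primary endpoints are defined.

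**Conclusion.** The concern holds. The printed counts and the stated operating characteristics contradict each other: exact alpha is 0.70 against 0.05, a factor of 14. Across assumed true proportions from 1% to 5% the stopping probability runs from 0.19 to 0.70, about 4 to 14 times the stated value, with no excess over the 5% the rule is meant to detect.

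The calculation treats recurrence as a binary outcome known for each patient at the look, with independent patients and cumulative counts. The proportion expected at one year is not in the documents, so no single practical false-stop risk can be given. The defect in the stated alpha does not depend on it. Because the rule governs closure of the whole trial, it must be corrected.

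**What to change.** Retrieve the EAST output first, to see whether counts or looks were mis-transcribed. Then recompute the boundary by exact binomial calculation, with the last look at the planned 104 patients, and print in Section 14.5 the cumulative counts, attained overall alpha, alternative proportion and power.

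Rounding a normal-theory Pocock limit up to whole events is not enough on its own: ≥4, 6, 7, 9, 10 has exact alpha 0.070 with the last look at 104. Purely to show that a conforming set exists, ≥4/21, ≥6/42, ≥8/63, ≥10/84, ≥11/104 has exact alpha 0.043, with power 0.55 at an assumed 10% and 0.77 at 12%. How much excess to tolerate is for the sponsor and DSMC to decide.

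If action on a single event among the first 21 is intended, describe it as a trigger for DSMC review and remove the alpha 0.05 claim. In either case, reconcile Sections 8.2, 13.2 and 14.5 on whether the rule mandates or permits stopping, and on what it reacts to.

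The cost is one rewritten paragraph and matching wording in two sections. No extra visits or data are needed. No extra patients are needed either, provided the power attainable with 104 is accepted; the example set falls short of 0.62 if the unstated alternative was 10%.

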APPENDIX 1 – COMMON TOXICITY CRITERIA

Acute Toxicity from *Common Terminology Criteria for Adverse Events v3.0 (CTCAE)*, Published: August 9, 2006

	Grade 0	Grade 1	Grade 2	Grade 3	Grade 4
FATIGUE	No change	Mild fatigue over baseline	Moderate or causing difficulty performing some ADL	Severe fatigue interfering with ADL	Disabling
RADIATION DERMATITIS	No change	Faint erythema or dry desquamation	Moderate to brisk erythema; patchy moist desquamation, mostly confined to skin folds and creases; moderate edema	Moist desquamation other than skin folds and creases; bleeding induced by minor trauma or abrasion	Skin necrosis or ulceration of full thickness dermis; spontaneous bleeding from involved site
PAIN	No pain	Mild pain not interfering with function	Moderate pain; pain or analgesics interfering with function, but not interfering with ADL	Severe pain; pain or analgesics severely interfering with ADL	Disabling

Table 1. RTOG/EORTC and LENT/SOMA classification of late effects

RTOG/EORTC	Grade 1	Grade 2	Grade 3	Grade 4
Skin	Slight atrophy, pigmentation change, some hair loss	Patchy atrophy, moderate telangiectasia, total hair loss	Marked atrophy, gross telangiectasia	Ulceration
Subcutaneous tissue	Slight induration (fibrosis), and loss of subcutaneous fat	Moderate fibrosis, but asymptomatic; slight field contracture, $\leq 10\%$ linear reduction	Severe induration and loss of subcutaneous tissue, field contracture, $\geq 10\%$ linear reduction	Necrosis
LENT/SOMA				
Breast				
Subjective				
Pain	Occasional and minimal Hypersensation, pruritus	Intermittent and tolerable	Persistent and intense	Refractory and excruciating
Objective				
Telangiectasia	$<1\text{ cm}^2$	$1\text{--}4\text{ cm}^2$	$>4\text{ cm}^2$	
Fibrosis	Barely palpable, increased density	Definite increased intensity and firmness	Very marked density, retraction, and fixation	
Edema	Asymptomatic	Symptomatic	Secondary dysfunction	
Retraction, atrophy	10–25%	$>25\text{--}40\%$	$>40\text{--}75\%$	Whole breast
Ulcer	Epidermal only, $<1\text{ cm}^2$	Dermal only, $>1\text{ cm}^2$	Subcutaneous	Bone exposed, necrosis
Lymphedema, arm circumference	2–4-cm increase	$>4\text{--}6\text{-cm}$ increase	$>6\text{-cm}$ increase	Useless arm
Skin				
Pigmentation change	Transitory, slight	Permanent, marked	—	—

Abbreviations: RTOG = Radiation Therapy Oncology Group; EORTC = European Organization for Research and Treatment of Cancer; LENT = Late Effects Normal Tissue Task Force; SOMA = subjective, objective, management, and analytic.

APPENDIX 2 – TOXICITY TRACKING FORM

Department of Radiation Oncology
NYU Hospitals Center
[name]
New York, NY 10016

PHYSICIAN'S PROGRESS NOTE

Fraction: 1-5 6-10 11-15 45-60 day F/U

The following critical elements of the patient's weekly exam have been covered:

- Chart & Dosimetry, Treatment set up & positioning review*
- Port Film or image review*
- Examination of patient for evaluation and progress of treatment (see notes below)*

Progress note: _____

Please indicate Toxicity due to Radiation Treatment on the following chart:

	Grade 0	Grade 1	Grade 2	Grade 3	Grade 4
FATIGUE					
	No change	Mild fatigue over baseline	Moderate or causing difficulty performing some ADL	Severe fatigue interfering with ADL	Disabling
RADIATION DERMATITIS					
	No change	Faint erythema or dry desquamation	Moderate to brisk erythema; patchy moist desquamation, mostly confined to skin folds and creases; moderate edema	Moist desquamation other than skin folds and creases; bleeding induced by minor trauma or abrasion	Skin necrosis or ulceration of full thickness dermis; spontaneous bleeding from involved site
PAIN (Breast)					
	No pain	Mild pain not interfering with function	Moderate pain; pain or analgesics interfering with function, but not interfering with ADL	Severe pain; pain or analgesics severely interfering with ADL	Disabling

Attending Signature: _____ Date: _____

APPENDIX 3 – QUALITY OF LIFE QUESTIONNAIRES

**NYU 09-0623 Phase I-II Study of Prone
Accelerated Breast and Nodal IMRT
Quality of Life Questionnaire - Baseline**

Form QLB (01-25-2005)
Page 1 of 7

Patient Initials ,
Last First Middle

Patient Study ID

Participants should complete this questionnaire at baseline (after consent). The first page is to be completed by a clinical staff member. Fill in the items listed on this page, print the patient's study ID at the top of pages 2 through 7 and give the questionnaire to the patient for completion. After the patient has completed the questionnaire, verify that the date has been recorded at the top of page 2.

Please administer the questionnaire at an office visit if possible. If that is not possible, mail the questionnaire to the patient, then call to ask for the patient's responses over the phone. If all efforts to administer the scheduled questionnaire fail, a B-39 QMD form should be submitted instead.

Mark Circles Like This: → ●

Institution Name / Affiliate Name

Staff Member Administering Form

171

Last Name

First Name

Phone

Are data amended? Yes (If yes, circle the amended items.)

[figure not shown]
Time point for this questionnaire (Do not mark in this box.)

- Baseline (after consent)

This form is being filled out: (Mark one.)

 By participant in doctor's office	 By clinical staff, on phone with participant
 By participant not in doctor's office	 Other

Record the participant's study ID on each of the remaining pages before giving the questionnaire to the participant.

Patient
Study ID Date this questionnaire is completed:
Month Day Year*(For example, if you were completing the questionnaire on September 8, 2004, you would write 09 08 2004 in the boxes.)*

Thank you for completing this questionnaire.

We are interested in your evaluation of your physical appearance and functioning since you have been treated for breast cancer. Please rate the following items on this four-point scale, according to your evaluation at this point in time.

	Difference between treated and untreated breast and area			
	None	Slight	Moderate	Large
1 Breast size	1	2	3	4
2 Breast texture (hardening)	1	2	3	4
3 Arm heaviness	1	2	3	4
4 Nipple appearance	1	2	3	4
5 Shoulder movement	1	2	3	4
6 Arm movement	1	2	3	4
7 Breast pain	1	2	3	4
8 Ability to lift objects	1	2	3	4
9 Fit of shirt sleeve	1	2	3	4
10 Breast tenderness	1	2	3	4
11 Shoulder stiffness	1	2	3	4
12 Breast shape	1	2	3	4
13 Breast elevation (how high the breast is)	1	2	3	4
14 Scar tissue	1	2	3	4
15 Shoulder pain	1	2	3	4
16 Arm pain	1	2	3	4
17 Arm swelling	1	2	3	4
18 Breast swelling	1	2	3	4
19 Arm stiffness	1	2	3	4
20 Fit of bra	1	2	3	4
21 Breast sensitivity	1	2	3	4
22 Fit of clothing	1	2	3	4

Patient
Study ID

--	--	--	--	--	--	--	--	--	--

We are interested in your personal reactions to the surgery you have received for your breast cancer. Please answer the following questions by circling one (1) number. Please note that the response options are labeled at the end-points only. However, you can and should use all of the points on the scale as appropriate to best convey your response.

1. To what extent has your surgery **disrupted** your normal daily activities?

0	1	2	3	4	5	6	7	8	9	10
Not at all										A lot

2. To what extent has your surgery **disrupted** your normal recreational activities?

0	1	2	3	4	5	6	7	8	9	10
Not at all										A lot

3. To what extent has your surgery **disrupted** your normal activities with your family and friends?

0	1	2	3	4	5	6	7	8	9	10
Not at all										A lot

4. To what extent has your surgery **disrupted** your normal sleep pattern?

0	1	2	3	4	5	6	7	8	9	10
Not at all										A lot

5. To what extent has your surgery **reduced** your enjoyment of life?

0	1	2	3	4	5	6	7	8	9	10
Not at all										A lot

6. To what extent has your surgery **disrupted** your regular activities at work (e.g., need to take time off, not getting done as much as you'd like)? If you do not work outside the home for pay, please check this box and go to the next question.

0	1	2	3	4	5	6	7	8	9	10
Not at all										A lot

7. How **satisfied** are you with the length of time your treatment has taken to this point in time?

0	1	2	3	4	5	6	7	8	9	10
Not at all										A lot

8. How **disruptive** has your surgery been to the other important people in your life (e.g., family and close friends)?

0	1	2	3	4	5	6	7	8	9	10
Not at all										A lot

 Convenience of Care (baseline version)  

Patient
Study ID

These questions are about how you feel and how things have been with you during the past 4 weeks. For each question, please give the one answer that comes closest to the way you have been feeling.

How much of the time during the past 4 weeks...

	All of the time	Most of the time	Some of the time	A little of the time	None of the time
1. Did you feel full of life?	1	2	3	4	5
2. Did you have a lot of energy?	1	2	3	4	5
3. Did you feel worn out?	1	2	3	4	5
4. Did you feel tired?	1	2	3	4	5

5. Rate your pain at its worst in the past four weeks. (Circle one number.)

0	1	2	3	4	5	6	7	8	9	10
---	---	---	---	---	---	---	---	---	---	----

No pain

Pain as bad as you
can imagine

6. Rate your pain at its least in the past four weeks. (Circle one number.)

0	1	2	3	4	5	6	7	8	9	10
---	---	---	---	---	---	---	---	---	---	----

No pain

Pain as bad as you
can imagine

7. Rate your pain on average in the past four weeks. (Circle one number.)

0	1	2	3	4	5	6	7	8	9	10
---	---	---	---	---	---	---	---	---	---	----

No pain

Pain as bad as you
can imagine

8. Rate how much pain you have right now. (Circle one number.)

0	1	2	3	4	5	6	7	8	9	10
---	---	---	---	---	---	---	---	---	---	----

No pain

Pain as bad as you
can imagine

9. Are you currently receiving treatments or taking medications for your pain?

Circle one: Yes No

Patient
Study ID

By circling one (1) number per line, please indicate how much you have been bothered by each of the following problems in the past four weeks.

	Not bothered at all	A little bit bothered	Some- what bothered	Bothered quite a bit	Bothered very much
Fever or shivering (shaking, chills)	0	1	2	3	4
Swelling of breast (breast feels larger)	0	1	2	3	4
Breast heaviness	0	1	2	3	4
Breast warm to touch	0	1	2	3	4
Breast skin is red	0	1	2	3	4
Breast skin is tanned	0	1	2	3	4
Breast skin or area around nipple is pale in color	0	1	2	3	4
Breast skin is flaking or peeling	0	1	2	3	4
Bleeding or fluid leakage from breast	0	1	2	3	4
Breast itching	0	1	2	3	4
Blisters on the breast (or breast skin moist and raw)	0	1	2	3	4
Coughing	0	1	2	3	4
Difficulty breathing	0	1	2	3	4
Muscle aches	0	1	2	3	4
Rib or chest wall pain	0	1	2	3	4
Infections	0	1	2	3	4
Slow healing of breast wounds	0	1	2	3	4
Visible small blood vessels (spider veins)	0	1	2	3	4
Pockmarks or puncture wounds on breast	0	1	2	3	4
Thickening of breast skin	0	1	2	3	4
Hardening of breast	0	1	2	3	4
Breast or nipple numbness	0	1	2	3	4
Sharp shooting pains or twinges in the breast	0	1	2	3	4

Patient Study ID

By circling one (1) number per line, please indicate how much you have been bothered by each of the following problems in the past four weeks.

	Not bothered at all	A little bit bothered	Some- what bothered	Bothered quite a bit	Bothered very much
Breast aches	0	1	2	3	4
Breast tenderness	0	1	2	3	4
Decrease or lack of arousal on breast	0	1	2	3	4
Any other problems? (Specify below)	0	1	2	3	4

Specify other problems:

You have been treated with breast conserving therapy for breast cancer. As you know, a reason for choosing this treatment is to keep a breast that looks and feels as close to normal as possible. Your opinion concerning the appearance of your breast is valuable to us. Circle the number next to the word that best describes how your breast looks now.

1	EXCELLENT: when compared to the untreated breast or the original appearance of the breast, there is minimal or no difference in the size or shape of the treated breast. The way the breast feels (its texture) is the same or slightly different. There may be thickening, scar tissue or fluid accumulation within the breast, but not enough to change the appearance.
2	GOOD: there is a slight difference in the size or shape of the treated breast as compared to the opposite breast or the original appearance of the treated breast. There may be some mild reddening or darkening of the breast. The thickening or scar tissue within the breast causes only a mild change in the shape or size.
3	FAIR: obvious differences in the size and shape of the treated breast. This change involves a quarter or less of the breast. There can be moderate thickening or scar tissue of the skin and the breast, and there may be obvious color changes.
4	POOR: marked change in the appearance of the treated breast involving more than a quarter of the breast tissue. The skin changes may be obvious and detract from the appearance of the breast. Severe scarring and thickening of the breast, which clearly alters the appearance of the breast, may be found.

My satisfaction about the treatment and results is: (Select the phrase that best describes your satisfaction.)

				
Totally satisfied	Somewhat satisfied	Neither satisfied nor dissatisfied	Somewhat dissatisfied	Totally dissatisfied

Patient
Study ID

Before any treatment to your breast, the size of your breasts was: (Select the phrase that best describes your breast size prior to treatment.)

 Larger
on left The same on
both sides Larger
on right

The size of your breasts now is: (Select the phrase that best describes your breast size now.)

 Larger
on left The same on
both sides Larger
on right

Thank you for completing this questionnaire!

**NYU 09-0623 Phase I-II Study of Prone
Accelerated Breast and Nodal IMRT**
Quality of Life Questionnaire - Follow-up

Form QLF(01-25-2005)
Page 1 of 6

Patient Initials ,
Last First Middle

Patient Study ID

Patients who experience a documented cancer recurrence or second primary cancer are not expected to complete questionnaires after that event. Patients who discontinue therapy for other reasons are expected to complete all the quality of life assessments.

The first page is to be completed by a clinical staff member. Fill in the items listed on this page, print the patient's study ID at the top of pages 2 through 6 and the assessment time point at the bottom of pages 1 through 6 and give the questionnaire to the patient for completion. After the patient has completed the questionnaire, verify that the date has been recorded at the top of page 2.

Please administer the questionnaire at an office visit if possible. If that is not possible, mail the questionnaire to the patient, then call to ask for the patient's responses over the phone. If all efforts to administer the scheduled questionnaire fail, a B-39 QMD form should be submitted instead.

Institution Name / Affiliate Name

Staff Member Administering Form

Last Name

First Name

Phone

Are data amended? Yes (If yes, circle the amended items.)

This form is being filled out: (Mark one.)

By participant in doctor's office

By clinical staff, on phone with participant

By participant not in doctor's office

Other

Mark Circles Like This: → ●

assessment time point End of RT Day 45-60 2 years

Record the assessment time point and participant's Study ID on each of the remaining pages before giving the questionnaire to the participant.

Patient Study ID

Date this questionnaire is completed:
 Month Day Year

(For example, if you were completing the questionnaire on September 8, 2004, you would write 09 08 2004 in the boxes.)

Thank you for completing this questionnaire.

We are interested in your evaluation of your physical appearance and functioning since you have been treated for breast cancer. Please rate the following items on this four-point scale, according to your evaluation at this point in time.

**Difference between treated and untreated
breast and area**

	None	Slight	Moderate	Large
1 Breast size	1	2	3	4
2 Breast texture (hardening)	1	2	3	4
3 Arm heaviness	1	2	3	4
4 Nipple appearance	1	2	3	4
5 Shoulder movement	1	2	3	4
6 Arm movement	1	2	3	4
7 Breast pain	1	2	3	4
8 Ability to lift objects	1	2	3	4
9 Fit of shirt sleeve	1	2	3	4
10 Breast tenderness	1	2	3	4
11 Shoulder stiffness	1	2	3	4
12 Breast shape	1	2	3	4
13 Breast elevation (how high the breast is)	1	2	3	4
14 Scar tissue	1	2	3	4
15 Shoulder pain	1	2	3	4
16 Arm pain	1	2	3	4
17 Arm swelling	1	2	3	4
18 Breast swelling	1	2	3	4
19 Arm stiffness	1	2	3	4
20 Fit of bra	1	2	3	4
21 Breast sensitivity	1	2	3	4
22 Fit of clothing	1	2	3	4

assessment time point End of RT Day 45-60 2 years

Patient Study ID

These questions are about how you feel and how things have been with you during the past 4 weeks. For each question, please give the one answer that comes closest to the way you have been feeling.

How much of the time during the past 4 weeks...

	All of the time	Most of the time	Some of the time	A little of the time	None of the time
1. Did you feel full of life?	1	2	3	4	5
2. Did you have a lot of energy?	1	2	3	4	5
3. Did you feel worn out?	1	2	3	4	5
4. Did you feel tired?	1	2	3	4	5

5. Rate your pain at its worst in the past four weeks. (Circle one number.)

0	1	2	3	4	5	6	7	8	9	10
---	---	---	---	---	---	---	---	---	---	----

No pain

Pain as bad as you can imagine

6. Rate your pain at its least in the past four weeks. (Circle one number.)

0	1	2	3	4	5	6	7	8	9	10
---	---	---	---	---	---	---	---	---	---	----

No pain

Pain as bad as you can imagine

7. Rate your pain on average in the past four weeks. (Circle one number.)

0	1	2	3	4	5	6	7	8	9	10
---	---	---	---	---	---	---	---	---	---	----

No pain

Pain as bad as you can imagine

8. Rate how much pain you have right now. (Circle one number.)

0	1	2	3	4	5	6	7	8	9	10
---	---	---	---	---	---	---	---	---	---	----

No pain

Pain as bad as you can imagine

9. Are you currently receiving treatments or taking medications for your pain?

Circle one: Yes No

assessment time point End of RT Day 45-60 2 years

1-4: SF - 36 v2 Vitality and 5-9: BPI Copyright 1991 [name]. Pain Research Group Used by permission.

Patient Study ID

By circling one (1) number per line, please indicate how much you have been bothered by each of the following problems in the past four weeks.

	Not bothered at all	A little bit bothered	Some- what bothered	Bothered quite a bit	Bothered very much
Fever or shivering (shaking, chills)	0	1	2	3	4
Swelling of breast (breast feels larger)	0	1	2	3	4
Breast heaviness	0	1	2	3	4
Breast warm to touch	0	1	2	3	4
Breast skin is red	0	1	2	3	4
Breast skin is tanned	0	1	2	3	4
Breast skin or area around nipple is pale in color	0	1	2	3	4
Breast skin is flaking or peeling	0	1	2	3	4
Bleeding or fluid leakage from breast	0	1	2	3	4
Breast itching	0	1	2	3	4
Blisters on the breast (or breast skin moist and raw)	0	1	2	3	4
Coughing	0	1	2	3	4
Difficulty breathing	0	1	2	3	4
Muscle aches	0	1	2	3	4
Rib or chest wall pain	0	1	2	3	4
Infections	0	1	2	3	4
Slow healing of breast wounds	0	1	2	3	4
Visible small blood vessels (spider veins)	0	1	2	3	4
Pockmarks or puncture wounds on breast	0	1	2	3	4
Thickening of breast skin	0	1	2	3	4
Hardening of breast	0	1	2	3	4
Breast or nipple numbness	0	1	2	3	4
Sharp shooting pains or twinges in the breast	0	1	2	3	4

assessment time point End of RT Day 45-60 2 years

SCL

Patient Study ID

By circling one (1) number per line, please indicate how much you have been bothered by each of the following problems in the past four weeks.

	Not bothered at all	A little bit bothered	Some- what bothered	Bothered quite a bit	Bothered very much
Breast aches	0	1	2	3	4
Breast tenderness	0	1	2	3	4
Decrease or lack of arousal on breast	0	1	2	3	4
Tattoos on breast placed for radiation therapy	0	1	2	3	4
Any other problems? (Specify below)	0	1	2	3	4

Specify other problems:

You have been treated with breast conserving therapy for breast cancer. As you know, a reason for choosing this treatment is to keep a breast that looks and feels as close to normal as possible. Your opinion concerning the appearance of your breast is valuable to us. Circle the number next to the word that best describes how your breast looks now.

1	EXCELLENT: when compared to the untreated breast or the original appearance of the breast, there is minimal or no difference in the size or shape of the treated breast. The way the breast feels (its texture) is the same or slightly different. There may be thickening, scar tissue or fluid accumulation within the breast, but not enough to change the appearance.
2	GOOD: there is a slight difference in the size or shape of the treated breast as compared to the opposite breast or the original appearance of the treated breast. There may be some mild reddening or darkening of the breast. The thickening or scar tissue within the breast causes only a mild change in the shape or size.
3	FAIR: obvious differences in the size and shape of the treated breast. This change involves a quarter or less of the breast. There can be moderate thickening or scar tissue of the skin and the breast, and there may be obvious color changes.
4	POOR: marked change in the appearance of the treated breast involving more than a quarter of the breast tissue. The skin changes may be obvious and detract from the appearance of the breast. Severe scarring and thickening of the breast, which clearly alters the appearance of the breast, may be found.

assessment time point End of RT Day 45-60 2 years

Patient Study ID

My satisfaction about the treatment and results is: (Select the phrase that best describes your satisfaction.)

 Totally satisfied Somewhat satisfied Neither satisfied nor dissatisfied Somewhat dissatisfied Totally dissatisfied

Before any treatment to your breast, the size of your breasts was: (Select the phrase that best describes your breast size prior to treatment.)

 Larger on left The same on both sides Larger on right

The size of your breasts now is: (Select the phrase that best describes your breast size now.)

 Larger on left The same on both sides Larger on right

Thank you for completing this questionnaire!

assessment time point End of RT Day 45-60 2 years

NYU 09-0623 Phase I-II Study of Prone Accelerated Breast and Nodal IMRT

Form QMD (01-25-2005)
Page 1 of 1

Missing Data Form for Quality of Life Questionnaire

Submit this form whenever a protocol-scheduled Quality of Life (QOL) Questionnaire (i.e., Form QLT, QLP, or QLF) is not filled out by the patient and the assessment cannot be obtained by phone or mail. No missing data form is required for partially completed QOL forms or patients who have died or had a documented breast cancer recurrence or a second primary cancer.

Patient Initials	 ,  	Last First Middle	Patient ID	
Institution Name / Affiliate Name			/	
Person Completing Form				
Today's Date	  Month	  Day	    Year	Last Name _____ First Name _____ Phone _____
Are data amended? (check box if yes, and circle amended items)  Yes				

Time Point for this Form (mark one)	
 Form QLT: Last day of radiation therapy	
 Form QLP: 45- 60 days after start of radiation therapy	
 Form QLF: 2 years after radiation therapy	

Reason QOL was Not Assessed During Clinic Visit (Mark the main reason and add comments below.)
 
  Staff oversight or understaffing  Staff concerned for patient's medical or emotional condition  Patient stated that she was too ill or upset to complete questionnaire  Patient refused to complete questionnaire for reason other than illness or upset  Patient was unavailable (e.g., scheduling or transportation difficulties) 	

Reason QOL was Not Obtained by Phone or Mail (Mark all that apply and add comments below.)
 
  Staff oversight or understaffing  Patient's medical or emotional condition  Patient refused to complete questionnaire  Staff was unable to contact patient by phone  Questionnaire was mailed to patient but she did not return it (for any reason) 	

Comments

Mark Circles Like This: → ●
